4. HYPOTHESES AND DECISION RULES

4.1. Statistical Hypotheses

There are no statistical hypotheses. The emphasis of the final analyses will be on estimation of key summary statistics.

4.2. Statistical Decision Rules

4.2.1. Part 1

Decision rules are based on calculating unit probability mass (UPM) of three dosing intervals corresponding to under, proper, and over dosing in terms of toxicity. Specifically, the underdosing interval is defined as $(0; J)T-e_1$, the over-dosing interval $(pr+e_2)$, and the proper-dosing interval $(pT-e_1, pr+e_2)$, where e_1 and e_2 are small fractions. For a target DLT rate of 0.275, the target equivalence interval is (0.225, 0.325). The three dosing intervals are associated with three different dose-escalation decisions (Table 1). The under-dosing interval corresponds to a dose escalation (E), over-dosing corresponds to a dose de-escalation (D), and proper-dosing corresponds to remaining at the current dose (S). Given a dosing interval and a probability distribution, the unit probability mass (UPM) is defined as the ratio of the probability of the interval to the length of the interval. Once the safety assessment is complete for Cycle 1 (ie, 28 days after the first dose), the focus will be on allocation of new subjects to the dose most likely to be an MTD.

The dose escalation in Part IA and JC, dose finding in Part JB, and each arm of the dose expansion in Part 2 of the study will stop as the applicable following criteria are met:

- *The maximum sample size has been achieved (approximately 75 patients in Part 1, excluding patients enrolled in biomarker cohorts, and approximately 70 patients in Part 2);*
- *6 to 12 evaluable patients (for Parts IA, Part 1B and Part 1C) that have been enrolled at a PF-06873600 dose level (as a single agent, in combination with letrozole, and in combination with fulvestrant, each) that is predicted to be the MTD per the mTPI method;*
- *All dose levels explored appear to be overly toxic, and the MTD cannot be determined.*

Specifically the mTPI approach formalizes stopping rules as follows:

Rule 1 (early termination): if the first dose is too toxic $\Pr(p_1 > PT | data) > \alpha$; $\alpha = 0.975$

Rule 2 (dose exclusion), if dose = i is too toxic $\Pr(p_i > PT | data) > \alpha$; $\alpha = 0.975$
then exclude doses i

4.2.2. Part 2

Part 2 dose expansion is an open-label, multi-center, non-randomized study to assess the preliminary anti-tumor activity and the safety and tolerability of PF-06873600. PF-06873600 will be administered at the RDE in 28 days cycles in combination with endocrine therapy in two separate dose expansion arms. Patients may be treated with IR or MR formulations depending on emerging data from Part 1 and availability.

Analyses may be performed on data from both Part 1 and Part 2 to explore the relationships between PK parameters, safety endpoints, and efficacy endpoints.

5. SAMPLE SIZE DETERMINATION

5.1. Part 1

In Part 1A, Part 1B and Part 1C, patients will participate in a dose escalation/finding phase aimed at estimating the MTD. The sample size for this component of the study will vary depending on the number of DLTs observed.

Approximately 75 patients are expected to be enrolled in the dose escalation/finding safety cohorts and an additional 6-12 patients are expected in the biomarker cohorts in Parts 1A and 1C. The actual number of patients enrolled will depend on the tolerability of PF-06873600 and the number of dose levels required to identify the MTD/IRDE. Part 1A, Part 1C and each independent combination cohort in Part 1B (PF-06873600 in combination with letrozole and PF-06873600 in combination with fulvestrant) can be stopped and MTD declared with approximately 6 to 12 patients. As for the number of patients treated at each dose, it is expected to be at 1 to 4 patients for the doses actually studied. However, since variable cohort size is allowed, the actual number of patients treated at each dose (including MTD) will vary from 1 to 12.

5.2. Part 2

Part 2, the expansion arms will be conducted to assess efficacy as well as safety and tolerability of PF-06873600 in single agent and combination therapy. The sample sizes for Part 2 are determined based on published historical data as benchmark data, 1-sided type I error rate of $\alpha = 0.1$ with 80% power or higher. Approximately 100 patients are expected to be enrolled in Part 2. Enrollment of participants into a given cohort may be discontinued if minimal or no anti-tumor activity is observed. CCI

I

I

- **CCI** [REDACTED]

6. ANALYSIS SETS

6.1. Safety analysis set

The safety analysis set includes all enrolled patients who receive at least one dose of study treatment.

6.2. Full analysis set

The full analysis set includes all enrolled patients.

6.3. Per-protocol analysis set (evaluable for MTD)

The per protocol analysis set includes all enrolled patients who receive at least one dose of study treatment and who do not have major treatment deviations during the first cycle. Patients with major treatment deviations during the first cycle of treatment are not evaluable for the MTD assessment and will be replaced as needed to permit the MTD estimation. Major treatment deviations include the failure to satisfy major entry criteria (eg, confirmation of the target disease, signed informed consent) or use of other anticancer treatments during the active treatment period and disease follow-up phases other than as defined/allowed in this protocol. Major treatment deviations will also include:

- *Administration of less than 75% of the planned number of doses of PF-06873600 during DLT observation period (provided that the reduction in doses is not due to toxicity attributable to PF-06873600).*
- *Administration of more than 110% of the planned number of doses of PF-06873600 during DLT observation period.*

6.4. Modified Intent-to-Treat (mITT) Population

- *The modified intent-to-treat (mITT) is the analysis population that will follow the ITT principle and include patients receiving at least 1 dose of investigational product with baseline assessment and at least 1 post baseline assessment, disease progression, or death before the first tumor assessment. The mITT population will be used for analyses and to support conference presentations when the study is still ongoing.*

6.5. Response Evaluable Set

The response evaluable population will include all participants who received at least one dose of study treatment and had baseline disease and at least one post baseline disease assessment.

6.6. PK analysis sets

The PK parameter analysis population is defined as all enrolled patients treated who have sufficient information to estimate at least 1 of the PK parameters of interest. The PK concentration population is defined as all enrolled patients who are treated and have at least 1 analyte concentration.

6.7. Biomarker analysis set(s)

- The PD/Biomarker analysis population is defined as all enrolled patients with PD/Biomarkers evaluated at pre-and/post dose.*

6.8. Treatment Misallocations

Patients who receive the wrong initial dose for whatever reason will be analyzed according to the initial dose actually received. Patients who receive the wrong dose after the initial dose will be analyzed according to the initial dose received.

6.9. Protocol Deviations

All deviations will be listed in the clinical study report (CSR). Major treatment deviations requiring a patient to be excluded from the MTD evaluation are in [Section 6.3](#).

7. ENDPOINTS AND COVARIATES

7.1. Efficacy Endpoint(s)

In this First In Patient study anti tumor activity is a primary objective for Part 2 of the study. Tumor response will be presented in the form of patient data listings that include, but are not limited to, tumor type, starting dose, tumor response at each visit, and best overall response. In addition, progression date, death date, date of first response and last tumor assessment date, and date of last contact will be listed. Objective response rate (ORR), progression free survival (PFS), overall survival (OS), time to progression (TTP), and duration of response (DOR) will be summarized and presented if data permits.

The above efficacy endpoints are derived based on the disease response per investigator evaluation on the CRF pages, which is the primary method of documentation of disease.

- Overall Response Rate (ORR)** - defined as the proportion of patients who achieved best overall response of complete response (CR) or partial response (PR) according to [Appendix 2 RECIST 1.1](#). Overall response is the best response recorded from first dose until disease progression/recurrence.

Unconfimed CR (uCR) is defined as one objective status of CR documented before PD, while confimed CR requires two objective statuses of CR a minimum of four weeks apart documented before PD. Sequences of CR - Non-evaluable - CR are considered confimed CR as long as the two CR responses are observed at a minimum of 4 weeks apart. Similarly, unconfimed PR (uPR) is defined as one objective status of PR documented before PD but not qualifying as uCR. Confimed PR is defined as two objective statuses of PR or better (PR followed by PR or PR followed by CR) a minimum of four weeks apart documented before PD, but not qualifying as CR. Sequences of PR - Stable Disease or Non-evaluable - PR are considered PRs as long as the two PR responses are observed at a minimum of 4 weeks apart. Based on these definitions, the unconfimed ORR analysis will include both confimed CR or PR and unconfimed CR or PR as responders, whereas the confimed ORR analysis will only include confimed CR or PR as responders.

- Progression Free Survival (PFS)** - is defined as the time from Cycle 1 Day 1 (CID1) to first documentation of disease progression or death due to any cause, whichever occurs first. Patients last known to be **1) alive** 2) on treatment or within the post-treatment follow-up period and 3) progression-free, are censored at the date of the last disease assessment that verified lack of disease progression. Patients who start new anti-cancer treatment prior to the end of post-treatment follow-up period and have adequate baseline and on-treatment objective disease assessments without evidence of progressive disease are censored at the date of the last objective disease assessment. Patients with inadequate baseline or no on-study disease assessments are censored at CID1 unless death occurred prior to the first planned assessment (in which case the death is an event). Patients with at least one on-study disease assessment who discontinue treatment without disease progression and without death within 28 days of discontinuation are censored at the date of the last objective disease assessment that verified lack of disease progression (if progression or death is within 28 days of discontinuation the progression or death is an event). Patients with documentation of progression or death after an unacceptably long interval (>16 weeks) since the previous disease assessment will be censored at the time of the previous assessment. If applicable, patients who are still ongoing at time of study termination by sponsor are censored at the date of study termination.

 $PFS \text{ (days)} = [\text{progression/death date} - \text{CID1} + \mathbf{1}]$.

If last adequate tumor assessment is within 6 months of CID1, any event of death or progression occurring after more than 18 weeks of last tumor assessment, then it qualifies for 2 missing and we censor at last adequate tumor assessment.

If last adequate tumor assessment is after 6 months and before 24 months of CID1, any event of death or progression occurring after more than 26 weeks of last tumor assessment, then it qualifies for 2 missing and we censor at last adequate tumor assessment.

If last adequate tumor assessment is after 24 months of CID1, any event of death or progression occurring after more than 4 months and 2 weeks of last tumor assessment, then it qualifies for 2 missing and we censor at last adequate tumor assessment.

- **Duration of Response (DOR):** Time from the date of first documentation of CR or PR to the date of first documentation of objective progression or death due to any cause.
- **Time to Progression (TTP):** Time from randomization until disease progression.

More details of censoring are provided in [Appendix 3](#).

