Appendix 8. Study Procedures After Primary Completion Date (PCD) Until End of
Trial..... 182

SCHEDULE OF ACTIVITIES (PART 1, PART 2 AND J-LIC)

The schedule of activities table provides an overview of the protocol visits and procedures. Refer to the [ASSESSMENTS](#) section of the protocol for detailed information on each assessment required for compliance with the protocol.

The investigator may schedule visits (unplanned visits) in addition to those listed in the schedule of activities in order to conduct evaluations or assessments required to protect the well-being of the patient.

See [Appendix 6](#) for alternative measures during public emergencies including the COVID-19 pandemic.

Protocol Activity	Screening	Active Treatment Phase [†] - One Cycle = 28 days					End of Treatment/ Withdrawal [§]	Post-Treatment Follow-Up [*]
		Cycles 1 and 2			Cycles ≥3			
Study Day	Within 28 days prior to registration unless specified otherwise	Day 1 [‡]	Day 8	Day 15	Day 21	Day 1		
Visit Window				±3 days	±3 days	±3 days	±5 days	
Informed Consent ¹	X							
Medical/Oncological History ²	X							
Baseline Signs/Symptoms ³		X						
Physical Examination ⁴	X						X	
Abbreviated Physical Examination ⁵		X	X	X	X	X		X
Vital Signs ⁶	X	X	X	X	X	X	X	X
Contraception Check ⁷	X	X				X	X	
ECOG Performance Status ⁸	X	X				X	X	X
12-Lead ECG ⁹	X	X	X C1 ⁹ and C2 ⁹	X C1 only		X	X	
Laboratory Studies¹⁰								
Hematology	X	X	X	X	X	X	X	(X)
Blood Chemistry	X	X	X ¹¹	X ¹¹	X ¹¹	X	X	(X)
Coagulation	X	X						(X)
Urinalysis	X						X	(X)
Pregnancy test	X	X				X	X	
Viral disease screening ¹²	X							
Disease Assessment								
Tumor markers (for breast cancer: CA 15-3 and CEA; Part 1 only for ovarian cancer: CA 125)	X	X				X	X	
CT/MRI Scans of Chest, Abdomen, Pelvis, any clinically indicated sites of	X	Performed every 8 weeks from C1D1 (±7 days) for the first 6 months, and then every 12 weeks (±7 days)					X ¹³	

Protocol Activity	Screening	Active Treatment Phase [†] - One Cycle = 28 days					End of Treatment/ Withdrawal [§]	Post-Treatment Follow-Up [*]
		Cycles 1 and 2				Cycles ≥3		
Study Day	Within 28 days prior to registration unless specified otherwise	Day 1 [‡]	Day 8	Day 15	Day 21	Day 1		
Visit Window			±3 days	±3 days	±3 days	±5 days		±7 days
disease, and of bone lesions; Clinical evaluation of superficial disease ¹³ Follow up for Overall Survival (OS)		thereafter for up to 2 years. After 2 years, performed every 4 months thereafter.						
Study Treatment								

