11.3. APPENDIX 3: CENSORING DETAILS**Table 6** Progression Free Survival and Duration of Response

Situation	Date of Progression/Censoring ¹	Outcome
Inadequate baseline assessment	Start date (CIDI)	Censored
No on-study assessments	Start date (CIDI)	Censored
Alive, on treatment ² and no Progression	Date of last objective tumor assessment	Censored
Progression Documented on or between scheduled tumor assessments prior to treatment discontinuation ²	Date of first objective tumor assessment showing objective progression	Progressed (Event)
Treatment discontinuation for undocumented progression	Date of last objective tumor assessment prior to discontinuation ²	Censored
Treatment discontinuation due to toxicity or other reason	Date of last objective tumor assessment prior to discontinuation ²	Censored
Death prior to first planned tumor assessment	Date of death	Death (Event)
Death without objective progression prior to treatment discontinuation ²	Date of death	Death (Event)
Death or progression after 2 or more missed tumor assessments	Date of last objective tumor assessment prior to the event	Censored
Ongoing at time of study termination by sponsor	Date of study termination	Censored

1: For date of censorship, if a tumor assessment takes place over a number of days (eg, superficial lesions one day, scans another), the last date is used as the assessment date.

2: or within 28 days of discontinuation of treatment.

Table 7 Time to Progression

Situation	Date of Progression/Censoring ¹	Outcome
Inadequate baseline assessment	Start date (CIDI)	Censored
No on-study assessments	Start date (CIDI)	Censored
Alive, on treatment ² and no Progression	Date of last objective tumor assessment	Censored
Progression Documented on or between scheduled tumor assessments prior to treatment discontinuation ²	Date of first objective tumor assessment showing objective progression	Progressed (Event)
Treatment discontinuation for undocumented progression	Date of last objective tumor assessment prior to discontinuation ²	Censored
Treatment discontinuation due to toxicity or other reason	Date of last objective tumor assessment prior to discontinuation ²	Censored
New anticancer treatment <28 days after discontinuation of treatment without progression	Date of last objective tumor assessment prior to new anticancer treatment	Censored
Death prior to first planned tumor assessment	Start date (CIDI)	Censored

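### SAP 7.1 censors PFS at Day 1 for an unscanned patient who dies on treatment after the week 8 scan date, and overlapping Table 6 rows give conflicting outcomes with no precedence

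*SAP*

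**What the plan says.** - **Endpoint (SAP 7.1).** PFS runs from C1D1 to "first documentation of disease progression or death due to any cause, whichever occurs first".
- **No on-study scan (SAP 7.1).** "Patients with inadequate baseline or no on-study disease assessments are censored at CID1 unless death occurred prior to the first planned assessment". A patient who dies that early counts as having had a PFS event.
- **Table 6 (SAP Appendix 3).** Three rows can apply to a patient who dies without a post-baseline scan:
  - "No on-study assessments": censored at the start date, with no exception inside the row.
  - "Death prior to first planned tumor assessment": event at the date of death.
  - "Death without objective progression prior to treatment discontinuation": event at the date of death. A footnote extends this to 28 days after stopping, and the row does not require a prior scan.
- **Missed scans.** Table 6 censors "Death or progression after 2 or more missed tumor assessments" at the last assessment before the event. SAP 7.1 gives two limits for the first 6 months: an interval of more than 16 weeks since the previous assessment, and more than 18 weeks since the last one as the mark of two missed scans.
- **Scan timing (Protocol, Schedule of Activities, CT/MRI row).** "Performed every 8 weeks from C1D1 (±7 days) for the first 6 months".
- **Status of PFS.** It is a secondary endpoint in Part 2, analysed in the Full Analysis Set (all enrolled patients). SAP 9.1 plans no formal hypothesis testing.

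**The concern.** A patient who was never rescanned and dies on treatment at week 10 has a known, dated PFS event under the endpoint definition. SAP 7.1 sets that patient's time to Day 1 and censors it, so the patient leaves the risk set before contributing any information. A missed scan followed by death is plausibly a sign of deterioration, so this censoring is likely to be informative.

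Two things are at stake. First, the PFS estimate is pushed upward from the date of the lost deaths. Second, two programmers could each follow Table 6 faithfully and produce different PFS results from the same data.

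**Working it through.** The documents state no PFS figure, event count or PFS-based sample size, so there is nothing to reproduce. The check has two parts: applying the rules to one type of patient, and an illustration of size on stated assumptions.

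**1. The rules applied**

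The patient has no post-baseline scan and no documented progression, and dies on treatment or within 28 days of stopping. With C1D1 as Day 1, the week 8 scan falls 8 × 7 = 56 days later, on Day 57. Its window runs from Day 50 to Day 64.

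| Time of death | SAP 7.1, no-scan sentence | Table 6, no-assessment row | Table 6, death rows | Missed-scan rules, if baseline counts as the previous assessment |
|---|---|---|---|---|
| Before week 8 | Event | Censored at C1D1 (row read alone) | Event (both rows) | Not triggered |
| Week 8 to about week 16-18 | Censored at C1D1 | Censored at C1D1 | Event (on-treatment death row) | Not triggered |
| After about week 16-18 | Censored at C1D1 | Censored at C1D1 | Event (on-treatment death row) | Censored |

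The clear problem is the middle band:

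- A death between Day 57 and Day 64 is censored at Day 1 although the scan could still have been done on time.
- A patient scanned at week 8 who dies at week 18 is an event, because 18 − 8 = 10 weeks is inside both missed-scan limits. An unscanned patient who dies at week 10 contributes nothing.

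**2. Size**

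Assumptions, none of them from the documents: exponential PFS with median M of 4, 6 or 9 months; no other censoring; k = 1, 2 or 3 affected deaths in Days 57-112. The arm sizes n = 30 and 40 are the planned Part 2 arms.

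At a time t after the affected deaths, the same number x of patients is still progression-free under either rule. Counting the deaths as events gives x/n. Censoring them at Day 1 gives x/(n − k). With S = x/n:

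rise in PFS(t) = x/(n − k) − x/n = S × k/(n − k)

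At 6 months S = 2^(−6/M), which is 0.354, 0.500 and 0.630 for M = 4, 6 and 9. For example, with M = 6, n = 40 and k = 2: 0.500 × 2/38 = 2.6 points.

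| n | k | M = 4 | M = 6 | M = 9 |
|---|---|---|---|---|
| 30 | 1 | 1.2 | 1.7 | 2.2 |
| 30 | 2 | 2.5 | 3.6 | 4.5 |
| 30 | 3 | 3.9 | 5.6 | 7.0 |
| 40 | 1 | 0.9 | 1.3 | 1.6 |
| 40 | 2 | 1.9 | 2.6 | 3.3 |
| 40 | 3 | 2.9 | 4.1 | 5.1 |

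Entries are percentage points of 6-month PFS. Simulated arms agree with them to within about 0.25 points.

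A worked case with n = 40, M = 6 and two unscanned deaths at week 10 leaves 19 patients progression-free at 6 months: 19/40 = 47.5% with the deaths as events, against 19/38 = 50.0% with Day 1 censoring.

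In simulation with M = 6 and k = 2, the median lengthens on average by about 19 days (n = 30) or 15 days (n = 40). The median moves in steps from one event time to the next, so these figures shift by a day or two with the convention used when the curve equals 0.5. The 6-month figures are the firmer measure.

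**Direction.** Before the affected deaths the curve is marginally lower, because the risk set has k fewer patients. From those deaths onward it can only be higher.

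**The case against.** The best defence is that SAP 7.1 addresses this patient specifically and picks an outcome, and that the Table 6 no-assessment row agrees with it. A reader might infer that Table 6 simply counts on-treatment deaths as events and that 7.1 contradicts it. The documents do not support that: the conflict is also inside Table 6, between rows that overlap without a ranking. What stands against the plan is that 7.1's choice departs from its own endpoint definition, and that the table alone does not settle the case.

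The affected group is also likely to be small. Protocol 7.4 calls for imaging whenever progression is suspected and at withdrawal from treatment (if not done in the previous 8 weeks). Entry requires ECOG 0 or 1 and excludes symptomatic visceral spread with a short-term risk of life-threatening complications. Death dates and last assessment dates are listed by patient, so any such case would be visible. PFS is secondary, nothing is formally tested, and no decision rule uses it. All of this stands and limits the consequence. The number of such deaths used in the illustration has no source in the documents.

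Finally, the argument from the missed-scan rules works only if baseline counts as the previous assessment, which the SAP does not say. That is correct, and it is a gap the fix has to close.

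**Conclusion.** The concern holds for one defined group: patients with no post-baseline scan who die on treatment, or within 28 days of stopping, after the first planned scan date. SAP 7.1 censors them at C1D1, against the PFS definition and against one Table 6 row, while another Table 6 row agrees with 7.1.

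A reader might go further and infer that the plan removes the earliest deaths from PFS. It does not: both SAP 7.1 and Table 6 expressly make a death before the first planned assessment an event.

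Under the assumptions above, 6-month PFS is overstated by about 1 to 7 points in arms of 30 to 40, and by nothing if no such death occurs. The impact is modest because PFS is a secondary, estimation-only endpoint. But the bias has a known direction from the affected deaths onward, and it comes from following the written rule exactly.

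**What to change.** In SAP 7.1 and Table 6:

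1. Limit the no-on-study-assessment rule to patients without a qualifying death, and state that the death rows take precedence over it. Say at the same time whether this also applies to the inadequate-baseline patients covered by the same 7.1 sentence.
2. Count as an event, at the date of death, any death on treatment or within 28 days of stopping that the two-missed-assessments rule does not exclude.
3. State that baseline (C1D1) counts as the previous assessment when there is no post-baseline scan.
4. Replace the conflicting limits of more than 16 and more than 18 weeks with a single limit.

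The cost is SAP wording and the matching derivation code; no new data are needed. The downside is that PFS becomes slightly less favourable if such deaths occur.
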